· · · · · · · · · · · · · · · · · · ·	Reaction

4 Introduction

4.1 Preface

Periportal fibrosis is the severest pathology caused by *Schistosomiasis mansoni* (1). The cornerstone of disease control is annual preventative chemotherapy (PC) through mass drug administration (MDA) of the safe and efficacious drug praziquantel (PZQ) (2). However, in areas of intense transmission ('hotspots') of the disease, MDA is failing to decrease infection intensity (3–5). Worryingly fibrotic patterns are not restricted to those of the older generation, ruling out the scenario that the fibrosis present is due to childhood exposure amongst those too old to have received treatment through MDA when they were school aged. This trial will investigate the effectiveness of increasing the number of treatment doses of PZQ given throughout the year in an infection hotspot on the prevalence of childhood periportal fibrosis. The standard annual dosing will be compared with two intervention arms, one with twice yearly dosing and one with four times yearly dosing.

4.2 Purpose of the analyses

The analysis will evaluate whether increasing treatment frequency with praziquantel through school-based /school-community based delivery strategies reduces the prevalence of childhood periportal fibrosis in schistosomiasis morbidity hot-spots after two years of intervention, comparing the standard one dose per year to two intervention arms, one with a twice yearly dosing and the other with a four yearly dosing.

5 Study Objectives and Endpoints

5.1 Study Objectives

(ICH E3; 8)

5.1.1 Primary objective

To compare the effect of 2x and 4x treatments annually with praziquantel to the standard 1x annual treatment on the prevalence of Schistosoma mansoni associated periportal fibrosis of the liver.

5.1.2 Secondary objective

To compare the effect of 2x and 4x treatments annually with praziquantel to the standard 1x annual treatment on the mean infection intensity of Schistosoma mansoni.

5.1.3 Exploratory objectives

Compare the effect of 2x and 4 x treatments annually with PZQ to the standard 1x annual treatment on the Egg Reduction Rate (ERR)

Compare the effect of 2x and 4 x treatments annually with PZQ to the standard 1x annual treatment on the point prevalence.

Compare the effect of 2x and 4 x treatments annually with PZQ to the standard 1x annual treatment on the cure rate.

Estimate the efficiency of using infection intensity to predict the occurrence of AE's.

5.2 Endpoints

(ICH E9: 2.2.2)

5.2.1 Primary endpoint

Periportal fibrosis measured at 2-years post 1st treatment follow up, defined as Niamey Protocol pattern scores of C, D, E or F = 1 v's A, B = 0 (scores X, Y & Z will not be analysed see section 8.4)

5.2.1.1 Secondary endpoint

• Schistosoma mansoni infection intensities as measured by Kato-Katz (KK) faecal egg counts (6), measured at 2-years post 1st treatment follow up

5.2.2 Exploratory endpoints

- Schistosoma mansoni Egg Reduction Rate (ERR) measured between:
 - Point Baseline and baseline +4 weeks
 - Baseline and 2 years + 4 weeks
 - o 2 years and 2 years +4 weeks
- Prevalence at 2 years post 1st treatment.
- Cure rate between:
 - Baseline and baseline +4 weeks
 - o Baseline and 24 months
 - Baseline and 24 months +4 weeks
- Adverse Events measured at baseline and 24 months:
 - Any AE (Yes/No)
 - Digestive AE's = 4,5,6,7,or 12 on CRF see Also section 11 of SAP (Yes / No)
 - Neurological AE's 1,2,3,8,9 or III on CRF see Also section 11 of SAP (Yes/No)

[figure not shown]
6 Study Methods

6.1 General Study Design and Plan

(ICH E3; 9)

This is a phase IV, randomised superiority trial that is blinded to the primary outcome assessors, but open label to all other investigators and participants. The control arm is the standard annual dose of praziquantel, intervention arm 1 is a twice yearly dose of praziquantel and intervention arm 2 is a four yearly dose of praziquantel. Randomisation will be 1:1:1 to each arm and stratified by school.

Trial Flow Chart

pathological responses.

Blood sample collection for monitoring of host immuno-

NB! Only 120 participants sampled at 12 months and only parasitology egg counts and only pre-treatment.

6.2 Inclusion-Exclusion Criteria and General Study Population

(ICH E3; 9.3. ICH E9; 2.2.1)

6.2.1 Inclusion Criteria

To be included in the trial the participant must:

- Have a parent/guardian who has given written/marked informed consent for the child to participate
- Have given written/marked informed assent to participate
- Be aged 6-14-years of age.
- Be born or resident within the community in which their school is situated for >=2 years.

6.2.2 Exclusion Criteria

The presence of any of the following will preclude participant inclusion:

- · History of facial oedema after treatment with praziquantel
- Known neurocysticercosis or intraocular cysticercosis

[figure not shown]
6.3 Randomisation and Blinding

(ICH E3; 9.4.3, 9.4.6, ICH E9; 2.3.1, 2.3.2)

Prior to enrolment trial participant identification numbers will be generated and these numbers assigned an intervention arm via simple computer generated random number randomisation. This paper-based list will be provided to the trial site team and upon enrolment children will be assigned to the ordered participant identification numbers, class-by- class and school-by-school and school-by-school or household-by- household if schools are not open. Randomisation will be stratified by school. The trial is open label to participants and the investigators, with the exception of the ultra-sonographers who are undertaking the scoring for the primary trial outcome. Scoring will be undertaken remotely from the participant being examined and the technicians conducting the exam.

6.4 Study Variables

(ICH E3; 9.5.1, ICH E9; 2.2.2)

 WHO ultrasonography Niamey protocol pattern scores – are a means of measuring periportal fibrosis. Ultrasonographic images of the liver parenchyma are compared with standard image patterns of liver parenchyma using annex A of 'A Practical Guide to the Standardized Use of Ultrasonography for the Assessment of Schistosomiasis—related Morbidity' and a score assigned as detailed below:

Pattern	Picture	IP-Score	
Α	Normal structure	0	
·	Patterns observed in schistosomiasis		
В	'Starry sky' (diffuse echogenic foci)	1	
C	Highly echogenic 'ring echoes', which correspond to the 'pipe stems' seen in a scan perpendicular to the one where rings are seen	2	
D	Highly echogenic ruff around portal bifurcation and main stem	.4	
E	Highly echogenic 'patches' extending' expanding? from the main portal vein and branches into the parenchyma	6 ⁻	
F	Highly echogenic 'bands' and 'streaks', extending from the main portal vein and its bifurcation to the liver surface, where they retract the organ surface. (Note: echogenic thickening of ligamenta alone does not justify assignment of the sonographic image to this pattern.)	8	
×	Diffusely coarse liver texture, irregular liver surface, distorted hepatic velos, rounded caudal liver edge	-	
Ÿ	Diffusely increased liver echogenicity, loss of highly reflective edges of peripheral portal branches, possibly distal sound extinction, rounded caudal liver edge	-	
Z.	All other liver abnormalities, specify		

Additional category created to accommodate participants who have a real and recorded fibrosis pattern of A|B OR B|A. Since there is no adjudication for these participants they will be recorded in summary statistic tables as A/B. This will not however have any impact on the primary endpoint since these individuals will still be classed as not having peri-portal fibrosis for the binary variable.

Ultrasonography will be conducted at the following time points:

- Baseline
- 24 months

Kato-Katz egg counts - this is a faecal thick microscopy smear used to calculate the Schistosoma mansoni eggs per gram of faeces. Up to three stool samples are collected at each of the following time points:

- Baseline
- Baseline + 4 weeks
- 12 months
- 24 months
- 24 months + 4 weeks

A maximum of six KK slides will be prepared from the three stool samples and the final egg counts recorded on the parasitology CRF for each visit are calculated as the mean of the total KK slides for that visit.

7 Sample Size

(ICH E3; 9.7.2, ICH E9; 3.5)

Berhe et al 2008 (7) reported a 47.7% resolution rate of grade C to non-periportal fibrosis scores of A and B and 24.6% resolution rates of D scores to scores A and B. Extrapolating this success rate onto our preliminary data, we would expect 35% less of the children in a successful intervention arm to have periportal fibrosis after 2 years intervention than those in the control arm. However, Berhe et al also reported geographical differences in resolution, with higher transmission villages having poorer resolution. We therefore propose a minimum 20% absolute difference in prevalence of periportal fibrosis between the control and intervention arms to be a clinically significant outcome. Based on preliminary data we assume an incidence rate of scores C-F of 80% in the control arm.

Initial sample size calculations used an adjusted alpha to allow for multiple testing using the Bonferoni correction – " a Bonferroni correction to allow any pairwise comparison between the three arms, testing at a 1.66% significance level, a total sample size of 450, 150 per arm, would provide 92% power to detect an absolute reduction of 20%." In previous Lake Victoria fishing community observation studies, failure to follow-up has been as high as 35%. The communities on Lake Albert are more stable ([name], pers. comm.) but to minimise failure to follow-up, selection was targeted at children in P1 to P4, retaining the cohort within the primary school structure over the two years of the study, and an inclusion criteria of born or resident in the village for >2yrs, displaying stability of their household within the village is included. Thus a lower estimate of failure to follow-up of 25% was included in the final study numbers giving a final sample size of 600.

The impact of COVID-19 on the study sample size however was a concern, some participants enrolled in the study were not located once the study had re-started as many had relocated due to the pandemic. Some "catch-up" enrolment beyond the initially aimed for 600 was conducted, however, tracing of the participants continued to be compounded by the fact that IMP administration was now happening in the community as schools had closed, and severe flooding and impacts of illegal fishing gear destruction by the government on parental livelihoods resulted in further community instability.

Also during the monitoring conducted by CCTU on behalf of the sponsor around 25% of participants in one of the primary schools had missing consent documentation. Where participants cannot be re-consented they will be withdrawn from the trial which may have an impact on the power of the study if the numbers are significant.

A gate-keeping approach to multiple testing was outlined in the Abstract SAP V1.0 and section 8.6 below, which allowed a significance level (alpha) of 5 % to be used as it is completely apportioned to each hypothesis in sequence and thus only used once and only if the significance criteria is met. A reduction of 20 % with 100 participants per arm would provide a power of 88%, a reduction of 25% would give 97% power and a 30% reduction would give 99% power.

8 General Considerations

8.1 Timing of Analyses

The final analysis will occur after the 24 month +4 week parasitology visits have taken place and all data from this visit has been entered into the macro database.

Version 1.0 of the SAP will be approved according to the requirements of CCTU/SOP023 before the data download. Permission to lock the database (softlock) will be requested by the chief investigator (CI) using CCTU/FRM094, and the data programmers will deposit the data in a folder to which the trial statistician is given access. Logical and graphical checks will be carried out to check that no out of range values are present. Data queries will be referred to the data management team for resolution (using CCTU/TPL064). Once all data queries have been resolved form CCTU/FRM094 will be signed off for database hardlock approval and at this point the final analysis report produced.

8.2 Analysis Populations

(ICH E3; 9.7.1, 11.4.2.5. ICH E9; 5.2)

8.2.1 Full Analysis Population

- All participants who were consented, eligible and randomised
- Any participant who had an ultrasound score of X,Y or Z at baseline will be withdrawn from the trial and is therefore not included in the 'Full Analysis Population'
- Any participants whose re-consent was required but not obtained are withdrawn from the trial and are not therefore included in the 'Full Analysis Population'

8.2.2 Safety Population

 All subjects who were consented and randomised and received any dose of the IMP irrespective of whether or not they were eligible.

8.3 Covariates and Subgroups

(ICH E3; 9.7.1, 11.4.2.1. ICH E9; 5.7)

School site was used to stratify randomisation and will be adjusted for as a fixed coefficient in the primary analysis.

Baseline Fibrosis score and egg count will be fixed effects in the model.

8.4 Missing Data

(ICH E3; 9.7.1, 11.4.2.2. ICH E9; 5.3. EMA Guideline on Missing Data in Confirmatory Clinical Trials)

The initial sample size calculation allowed for a 25% loss to follow up. However the power of the study has since been estimated based on a re-estimated prediction of the final sample size and a revised approach to multiple testing. If therefore the primary outcome data does not fall below 300 participants, then a complete case analysis of the data will be carried out. A graph to illustrate the proportion of the missing data for the primary and secondary endpoints as well as the baseline variables of periportal fibrosis and infection intensity (EPG) will be produced.

Data will be assumed to be missing at random (MAR) and appropriate sensitivity analysis conducted to assess the treatment effect for the primary analysis (8).

8.4.1 X, Y and Z scores for the primary efficacy analysis

The WHO ultrasonography Niamey protocol pattern scores include X, Y and Z which are not analysed in this trial as the liver patterns observed for these scores mean that it difficult to tell if there is periportal fibrosis due to Schistosoma.

At baseline any participant with these scores will be marked as 'unclassifiable and removed from cohort' they do not contribute any further data to the trial. They will be excluded from the Full Analysis Population.

Any participant with Ultrasonography scores of X, Y or Z at 2 years will be excluded from any analysis of the primary endpoint as missing data. This is because the number of participants is likely to be small, around 1% of the sample size.

Participants with X, Y and Z scores for the primary end point could however contribute data to the Secondary and exploratory endpoints.

8.4.2 Missing baseline data

There is a proportion of missing baseline WHO ultrasonography Niamey protocol pattern scores and egg count data. Only using cases with completed baseline data for these variables will significantly reduce the efficiency of the model as it may exclude outcome data which has been collected.

We will assume that whether the baseline data is collected or not is not associated with the treatment assigned. Missing baseline values will be calculated using predictive mean matching (egg count) or logistic regression (fibrosis score) imputation using the "mice" package in R. (9,10)

8.5 Interim Analyses and Data Monitoring

(ICH E3; 9.7.1, 11.4.2.3. ICH E9; 4.1, FDA Feb 2010 "Guidance for Industry Adaptive Design Clinical Trials for Drugs and Biologics")

No interim analysis will be required for this trial.

8.6 Multiple Testing

(ICH E3; 9.7.1, 11.4.2.5. ICH E9; 2.2.5)

To allow for multiple testing of the primary endpoint and control for the type I error rate (false positive error rate) a gatekeeping procedure will be used. The null hypothesis of no difference in the prevalence of periportal fibrosis will be tested for each of the following comparisons and compared to a significance level (α – alpha) of 5%:

[figure not shown]
H₁: - 4 x annual treatment of PZQ v's Standard 1x annual treatment

H₂: - 2 x annual treatment of PZQ v's Standard 1x annual treatment

H₃: - 4 x annual treatment of PZQ v's 2 x annual treatment

Each hypotheses will be tested *in sequence* and testing continues until the null hypothesis cannot be rejected i.e. a non-significant result is obtained (Fig 2), or all three comparisons are statistically significant. The sequential testing rules mean that the overall rate of any false positive across the three possible comparisons is constrained to be less than 5% (11).

Fig 2: Flow diagram to illustrate testing of hypotheses using gate-keeping procedure

This is a deviation from the multiple testing approach detailed in the protocol v 2.0. The justification is to use the ordering implied by the details of the dosing: so if the most frequent dosing cannot show an improvement in efficacy compared to the least frequent, then we can assume the intermediate dosing will not do so either, and there would be no value in carrying out formal inference. This approach will help to maintain the power of the most relevant questions, given the anticipated reduction in sample size due to movement of the population as a result of the COVID 19 pandemic and other impactful local conditions.

9 Summary of Study Data

All continuous variables will be summarised using the following descriptive statistics: n (non-missing sample size), mean, standard deviation, median, maximum and minimum. The frequency and percentages (based on the non-missing sample size) of observed levels will be reported for all categorical

measures. In general, all data will be listed, sorted by treatment and subject, and when appropriate by visit number within subject. All summary tables will be structured with a column for each treatment in the order (Standard of Care, Intervention 1 (2 x treatment), Intervention 2 (4 x treatment) / Total) and will be annotated with the total population size relevant to that table/treatment, including any missing observations.

The sample size of non-missing values for univariable summary statistics may be larger than the sample size used in the primary regression analysis.

[figure not shown]

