10.1 Primary Efficacy Analysis

The primary analysis will estimate the absolute difference between each intervention arm and the control arm in the proportion of participants with periportal fibrosis adjusting for the baseline covariates;

- School (Buhirigi / Kaiso)
- fibrosis score (A, B) /(C,D, E, F)

- egg count epg
- duration of residency (2-4 years / > 4 years)

A generalised linear model with a binomial distribution and an identity link function will be fitted (12,13). Standard errors and 95% confidence intervals will be estimated directly from the model.

Should convergence issues arise with the identity link, then a model will be fitted with a logistic link to ensure convergence. The g-formula will then be used to provide an estimate of the average absolute risk difference (12,14). Specifically, for each participant a predicted probability for *all three* arms, but using their original covariate values will be calculated; the within-participant absolute difference calculated; the average of the differences across the participant population will be taken. Bootstrapping will be used to provide a standard error, 95% confidence intervals and p-values.

Hypothesis testing of the null (H0) against the alternative hypothesis (H1) will provide two-sided p-values for each of the three pairwise comparisons between the treatment arms.

H₀: there is no difference in the proportion of participants with periportal fibrosis between treatment arms.

H₁: there is a difference in the proportion of participants with periportal fibrosis between treatment arms.

The multiple testing procedure detailed in section 8.6 will be used whereby the p-value for the first hypothesis is compared to a significance level of 5 % if p< 0.05 then the null hypothesis is rejected and the α can be passed to the next hypothesis in the sequence (Fig 2).

A minimum 20% absolute difference in prevalence of periportal fibrosis between the control and intervention arms would be considered a clinically significant outcome. Based on preliminary data an incidence rate of scores C-F of 80% in the control arm is assumed.

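### In the H1–H2–H3 sequence, a non-significant 2x v 1x result (H2) blocks the 4x v 2x test (H3); error control does not need this gate, and when 2x adds little it costs most of the power for H3

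*SAP*

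**What the plan says.** Section 8.6 lists three null hypotheses for the primary endpoint, in this order: H1 compares the 4x arm with the 1x arm, H2 compares 2x with 1x, and H3 compares the two intervention arms with each other.

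Each is held to a 5% level, and "testing continues until the null hypothesis cannot be rejected i.e. a non-significant result is obtained". Section 10.1 repeats the rule: when the first p-value is below 0.05, "the null hypothesis is rejected and the α can be passed to the next hypothesis in the sequence (Fig 2"). It also says the analysis will give "two-sided p-values for each of the three pairwise comparisons between the treatment arms". Fig 2 is not reproduced in the text at hand, but the wording is clear without it: H3 is formally tested only if H1 and H2 are both significant.

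The reason given in 8.6 is the ordering of the dosing. For the case where 4x fails to beat 1x, the section reasons: "then we can assume the intermediate dosing will not do so either, and there would be no value in carrying out formal inference". It adds that the approach should protect power for the most relevant questions as the sample shrinks.

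**The concern.** The rationale explains why H1 should come first and gate the rest. It does not explain why a non-significant H2 should stop H3. If 4x has beaten 1x and 2x has not been shown to, a difference between 4x and 2x is, if anything, more plausible. Yet in that situation the sequence ends before H3 is reached.

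What is at stake is the confirmatory claim on whether four treatments a year do better than two. The trial could reject H1, show a clear difference between 4x and 2x, and still be unable to claim H3 because H2, which has low power for a small 2x effect, fell short.

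**Working it through.** **Inputs from the SAP.** Two-sided tests (10.1) at 5% each (8.6); 100 per arm, control prevalence 80%, and a 20-point reduction as the design effect (section 7). The SAP states no 2x prevalence and no 4x v 2x difference, so all 2x values below are assumptions, shown as a range.

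**The plan's own power figure.** With a pooled two-proportion z-test,

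power = Φ{[d√n − 1.96√(2p̄(1−p̄))] / √(p₁(1−p₁) + p₂(1−p₂))}.

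For 80% v 60%: d√n = 0.2 × 10 = 2; p̄ = 0.70, so √(2 × 0.7 × 0.3) = 0.648; √(0.16 + 0.24) = 0.632. This gives Φ[(2 − 1.270)/0.632] = Φ(1.154) = 87.6%. Reductions of 25 and 30 points give 97.0% and 99.6%. The SAP states 88%, 97% and 99%, so its figures are reproduced.

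**Is the H2 gate needed for error control?** Write the nulls as H1: 4x = 1x; H2: 2x = 1x; H3: 4x = 2x. Any two of them imply the third, so exactly two true nulls is impossible. Consider the alternative rule: test H1 at 5%; if it is rejected, test H2 and H3 each at 5%.

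- H1 true (alone or with the other two): any false claim requires H1 to be falsely rejected first, so the probability is at most 5%.
- H1 false: at most one of H2 and H3 is true, and it is tested once at 5%.

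The familywise error is therefore at most 5% in every configuration, the same guarantee that 8.6 gives for its sequence. Exact enumeration of three binomial arms of 100 with pooled z-tests agrees (1x/2x/4x):

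| True prevalence, % | True null | Plan | H2 gate removed |
|---|---|---|---|
| 80/80/80 | all three | 5.1% | 5.1% |
| 80/80/60 | H2 | 3.9% | 3.9% |
| 80/60/60 | H3 | 2.6% | 3.8% |
| 80/20/20 | H3 | 5.1% | 5.1% |

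The 0.1 point above 5% is the z-test's own discreteness and is the same under both rules.

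**Power to claim H3.** Under the plan this is P(H1, H2 and H3 all significant); with the gate removed it is P(H1 and H3 significant). Same enumeration; the last column is 1 − plan/removed, from unrounded values:

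| 1x/2x/4x, % | Power of H2 alone | Plan | H2 gate removed | Share of H3 power lost |
|---|---|---|---|---|
| 80/80/60 | 5% (null true) | 3% | 80% | 97% |
| 80/75/60 | 14% | 4% | 59% | 93% |
| 80/70/60 | 37% | 5% | 31% | 83% |
| 80/65/60 | 67% | 4% | 11% | 67% |
| 80/70/50 | 37% | 26% | 83% | 69% |
| 80/65/45 | 67% | 51% | 83% | 38% |
| 80/60/50 | 88% | 23% | 31% | 25% |
| 80/60/40 | 88% | 71% | 83% | 14% |

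The first four rows use the SAP's 20-point effect for 4x. There, H3 power under the plan is no more than about 5% for any 2x prevalence between 60% and 80%. The power for H1 and H2 is the same under both rules, because H2 is still tested after H1 at 5%.

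**The case against.** **The plan is valid.** A fixed sequence controls the familywise error, and the claim in 8.6 is right. A reader might infer an error-control fault; there is none. The point is about efficiency.

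**H3 is secondary in importance.** The primary objective (5.1.1) compares 2x and 4x with 1x only, and 10.1 describes the primary estimate as each intervention arm against control. Putting H3 last fits that. This lowers the weight of the point but does not justify the gate: 8.6 places H3 in the confirmatory family, and releasing it takes nothing from H2.

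**The result is not hidden.** Section 10.1 produces p-values for all three pairs whatever the sequence does. What is lost is the formal claim.

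**The SAP does not say that a non-significant H2 leaves nothing worth testing.** It is tempting to read the sentence about there being no value in formal inference that way, but it concerns failure of H1 only. The fair criticism is that no reason is given for the H2 gate.

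**The gain is not always large.** If 4x achieves 20 points and 2x most of that, H3 has little power under either rule (80/65/60: 4% v 11%).

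**The 80% control prevalence may not hold.** Section 9.3.3 reports that very few participants had fibrosis in the 2020 baseline data, which came from one of the two schools. At 10/6/2% the figures are 1% v 24%: the direction is the same, the absolute power much lower.

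**The change would come late.** Sections 9.3.3, 10.2.2, 10.2.5, 16.1.5 and 16.1.7 record post hoc decisions and the handling of observed data. This stands and affects how the change must be made.

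**Conclusion.** The H2 gate on H3 is unnecessary, and the SAP gives no reason for it. Removing it keeps every claim the plan allows and the same 5% familywise bound.

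The size of the benefit is conditional. When 2x adds little over 1x, nearly all the H3 power is lost (97% of it at 80/80/60, 93% at 80/75/60). When 2x alone has a large effect, the loss is modest (25% at 80/60/50, 14% at 80/60/40). A reader might conclude that the plan always discards most of its power for H3; the figures do not support that.

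The error-control argument rests on logic alone. The power figures rest on 100 per arm, 80% in controls, unadjusted z-tests and assumed 2x prevalences. Covariate adjustment or a lower control prevalence would change them. This is a free improvement to a valid plan, not the correction of an error.

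**What to change.** In 8.6, 10.1 and Fig 2, replace the three-step chain with: test H1 at two-sided 5%; if it is rejected, test H2 and H3 each at two-sided 5%, neither conditional on the other. State why strong control holds: when 4x and 1x differ, H2 and H3 cannot both be true. Keep the dosing-order rationale for the H1 gate only.

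The cost is wording and a redrawn figure. No participants, data or models are added, since all three pairwise p-values are already planned. Because this SAP version already contains post hoc decisions, date the change. If outcome data by arm had been seen when it is made, label it post hoc and report the result under the sequence now in 8.6 alongside it.
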